3 STUDY OBJECTIVES

3.1 Primary Objective

The primary objective is to assess the clinical efficacy of whole blood compared to component therapy for trauma patients requiring massive transfusion, as measured by volume of blood products transfused within the first 24 hours of admission.

3.2 Secondary Objectives

The secondary objectives are to evaluate:

1. Functional coagulopathy as measured by thromboelastography;
2. 30-day mortality;
3. Number of units of blood products transfused by component/product;
4. Complications;
5. Hemolysis;
6. Wastage of blood units

See Section 5 for definitions of primary and secondary endpoints.

4 STUDY DESIGN

4.1 Study Overview

This is a single center, prospective cohort study. Enrollment of approximately 98 patients is planned, 49 receiving whole blood and 49 receiving component therapy. This is an observational study planned during initiation of a change in practice at our institution initially allowing up to 4 units of whole blood transfusion for adult male trauma patients. If initial patients receiving whole blood show no evidence of hemolysis and thrombocytopenia compared to patients receiving component therapy, up to 6 units of whole blood transfusion will be allowed (see below, and section 5.2, Safety Evaluations). Patients in the whole blood, or index, group are adult male trauma patients presenting in hemorrhagic shock (systolic blood pressure < 100) requiring massive transfusion activation who receive whole blood for resuscitation. Two control groups will be utilized. The prospective control group consists of adult male patients who present during times when whole blood is not available, as well as adult female patients, presenting in hemorrhagic shock (systolic blood pressure <100) requiring massive transfusion activation. Additionally, a second control group consisting of historical

PI: [name]

controls receiving component therapy will be analyzed (see Section 6, Patient Selection, for details of index and control groups).

All patients will have, in addition to standard labs, additional labs drawn for thromboelastography, platelet function determination, and coagulation factor levels (see Section 9.1.6, Other Clinical Procedures, for details of specific lab tests and timing).

Patients who meet all inclusion criteria and none of the exclusion criteria will be enrolled into the study.

Total duration of patient participation will be approximately 1 year (365 days), or the duration of the hospital stay, whichever is shorter. This includes up to 5 days of laboratory testing during initial resuscitation and subsequent admission, and up to one year of follow up via chart review if the patient remains in the hospital. Total duration of the study including recruitment and follow up is expected to be 2 years.

5 CRITERIA FOR EVALUATION

5.1 Primary Efficacy Endpoint

The primary objective is to assess the clinical efficacy of whole blood compared to component therapy for trauma patients requiring massive transfusion. Primary analysis will compare volume of blood transfusion within 24 hours of admission for patients without severe TBI (defined as GCS \leq 8 and imaging evidence of brain injury) for patients who received WB versus component therapy for initial resuscitation.

Secondary Efficacy Endpoints

The secondary objectives will evaluate the effect on survival; the development of multiple complications related to survival; and wastage data. The full list of secondary endpoints is as follows:

1. Volume of blood transfusion within 24 hours of admission for patients with severe TBI (GCS \leq 8 and imaging evidence of brain injury) and for entire cohort of patients.
2. Thromboelastography parameters including maximum amplitude, reaction time, alpha angle, fibrinolysis, and platelet function at 3 and 6 hours of resuscitation, after every 6 units of whole blood equivalent (WB or PRBCs) given, at the time of completion of resuscitation (time of last unit of blood product given), and on ICU days 1, 3 and 5.
3. 30-day mortality;

PI: [name]

4. Duration of need for renal replacement therapy, mechanical ventilation, ICU admission, and hospital stay;
5. Number of units of blood products transfused by component/product during first 24 hours of admission and total hospitalization;
6. Complications which include clinical coagulopathy, infection, venous thromboembolism, cerebrovascular accident, acute coronary syndrome, transfusion-related lung injury, transfusion-associated cardiac overload during total hospitalization;
7. Hemolysis as measured by haptoglobin, bilirubin, lactate dehydrogenase, and direct antiglobulin on ICU day 1;
8. Wastage of blood units

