9.1.7 Adverse Events

Information regarding occurrence of adverse events will be captured throughout the study. Duration (start and stop dates and times), severity/grade, outcome, treatment and relation to study drug will be recorded on the case report form (CRF).

Morbidity and mortality in this study population (patients requiring massive transfusion for trauma) is high.²⁹ Therefore we expect a relatively large number of adverse events, and resulting SAE reports, for reasons unrelated to the study.

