Total fluids received in the first 24 hours

Data collected on initial 5 days of hospitalization:

Vital signs: systolic and diastolic blood pressure, heart rate, respiratory rate, oxygen saturation, temperature

Hemoglobin

Hematocrit

PI: [name]

White blood cell count
Platelet count
Sodium
Potassium
Chloride
Bicarbonate
Blood urea nitrogen
Creatinine
Glucose
Aspartate transaminase (AST)
Alanine transaminase (ALT)
Total bilirubin
Direct bilirubin
Alkaline phosphatase
pH
Lactate
PaCO₂ (arterial CO₂ partial pressure)
PaO₂ (arterial oxygen partial pressure)
Base excess
Prothrombin time (PT)
INR
Partial thromboplastin time (PTT)
Fibrinogen
Thrombin
Antithrombin Complex
Factor V
Factor VII
Factor VIII
Factor X
D-dimer
Lactate dehydrogenase (LDH)

PI: [name]

Haptoglobin

Data collected on entire hospitalization:

Procedures performed during hospitalization

Operations performed during hospitalization

Discharge date

Disposition

Discharge capacity

Date and cause of death if applicable

Comorbidities

Admission medications

Total hospital and intensive care unit length of stay

Number of days on ventilator

Number of days on dialysis

Number of days on vasopressor medications

Number and nature of operative procedures

Development of venous thromboembolism

Development of acute kidney injury

Development of acute respiratory distress syndrome

Development of liver failure

Suspected or confirmed transfusion reaction

Hemolytic transfusion reaction

Transfusion associated lung injury

Development of cardiac failure

Development of clinical coagulopathy

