15.3 Analysis of Primary Endpoint

Primary analysis compares volume of blood products transfused in the first 24 hours of admission in patients without severe TBI (severe TBI is defined as GCS \leq 8 and evidence of brain injury on imaging) receiving whole blood versus component therapy during initial resuscitation.

For continuous variables including the primary endpoint, the statistical method will depend on the distribution of the data. If the data appears to follow a normal distribution, a t-test will be used, otherwise, a nonparametric Wilcoxon rank sum test will be used.

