15.4 Analysis of Secondary Endpoints

Continuous variables and categorical variables will be analyzed as described above (section 15.3). Mixed effects linear regression models will be used to evaluate coagulopathy over time and to adjust for confounding variables.

To analyze coagulopathy over time we will use a mixed effects linear regression model. A mixed effects linear regression model will also be used to adjust for confounding variables such as sex, age, comorbidities, severity of injury, and physiologic parameters of shock including pH and temperature, and use of a rapid transfuser (which more effectively warms blood).

Quarterly safety monitoring will compare categorical variables including mortality and development of complications (duration of need for renal replacement therapy,

PI: [name]

mechanical ventilation, ICU admission, and hospital stay; clinical coagulopathy, infection, venous thromboembolism, cerebrovascular accident, acute coronary syndrome, transfusion-related lung injury, transfusion-associated cardiac overload; transfusion reactions including clinical transfusion reactions and rates of hemolysis as measured by haptoglobin, bilirubin, lactate dehydrogenase, and direct antiglobulin). Categorical variables will be compared using the chi-squared test.

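### Secondary endpoint 4 compares raw days of support and stay with deaths included, so early deaths tend to favour the arm with more of them; section 15.4 also sends these durations to a chi-squared test

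*Protocol*

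**What the plan says.** Item 4 of the secondary efficacy endpoints (section 5.1, repeated in the synopsis) is "Duration of need for renal replacement therapy, mechanical ventilation, ICU admission, and hospital stay". It gives no fixed window and no rule for a patient who dies. The data list in section 10.1 matches it with simple counts: "Number of days on ventilator", "Number of days on dialysis" and "Total hospital and intensive care unit length of stay".

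For continuous variables section 15.3 states: "If the data appears to follow a normal distribution, a t-test will be used, otherwise, a nonparametric Wilcoxon rank sum test will be used". Section 15.4 carries this to the secondary endpoints by cross-reference. The analysis set in section 15.1 requires one or more units of blood and TEG testing; it does not exclude patients who die. 30-day mortality is a separate item (item 3) and is not joined to the durations. Section 9.1.7 says: "Morbidity and mortality in this study population (patients requiring massive transfusion for trauma) is high".

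Later in section 15.4, quarterly safety monitoring is to "compare categorical variables including mortality and development of complications (duration of need for renal replacement therapy". The bracket goes on to name ventilation, ICU admission and hospital stay, and the paragraph ends by assigning the chi-squared test to categorical variables.

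**The concern.** Death ends a count of days. If it comes before a survivor's stay would have ended, the patient contributes a short duration, and a t-test or rank test on the raw count treats that like an early recovery. Survival is one of the outcomes on which the two products may differ, so unequal deaths between arms are a real possibility and not a nuisance that balances out. A shorter ICU or hospital stay could then reflect more deaths.

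The second problem is one of consistency. A number of days is not categorical, no cut-point is given that would make it so, and the same variables already fall under the rule for continuous data in section 15.3.

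**Working it through.** The protocol states no figure for item 4, so there is none to reproduce.

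**Inputs from the protocol.** 49 patients per arm, about 31 without severe TBI (sample size text in section 15.5). Type I error 0.05, sidedness not stated and taken here as two-sided. Typical hospital stay about 14 days (synopsis), used as the survivors' mean.

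**Assumed, because the protocol gives none.** Mortality by arm, time to death, a standard deviation of 12 days for survivors' hospital stay, and the ICU averages in step 2.

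**Step 1: direction.** Let d be the proportion dying, S the mean duration in survivors and T the mean duration in those who die, with S and T equal in both arms.

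- Mean duration = (1 − d) × S + d × T
- Mean in A − mean in B = (d_B − d_A) × (S − T)

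If B has more deaths, B looks shorter when T < S, there is no difference when T = S, and B looks longer when T > S.

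**Step 2: ICU days, with S = 10 and T = 1 assumed.**

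- d = 0.20: 0.80 × 10 + 0.20 × 1 = 8.2
- d = 0.40: 0.60 × 10 + 0.40 × 1 = 6.4, so 1.8 days shorter with twice the mortality
- d = 0.25 v 0.30: 7.75 v 7.3, so 0.45 days shorter
- ICU-free days to day 30 with death = 0, (1 − d) × (30 − 10): 16.0 at 20% and 12.0 at 40%, which agrees with mortality

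**Step 3: hospital stay, with S = 14 and mortality 20% (A) v 40% (B).**

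- T = 3: 0.20 × (14 − 3) = 2.2 days shorter in B
- T = 14: 0.20 × 0 = 0
- T = 20: 0.20 × (14 − 20) = −1.2, so B is longer

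**Step 4: how often a test would show it.** Simulation of hospital stay, 3,000 replicates per scenario. Survivors' stay is lognormal (mean 14, SD 12) in both arms. Time to death is exponential with mean 1, 3 or 7 days, capped at the stay the patient would otherwise have had. Ranges run over the three mean times to death.

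| Per arm | Mortality A v B | B has shorter mean stay | B significantly shorter (Wilcoxon) |
|---|---|---|---|
| 49 | 20% v 20% | about 50% | 2–3% |
| 49 | 20% v 30% | 65–71% | 8–13% |
| 49 | 20% v 40% | 78–86% | 18–38% |
| 49 | 10% v 40% | 87–96% | 37–72% |
| 31 | 20% v 40% | 74–82% | 14–26% |

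In the rows with unequal mortality, A is significantly shorter in under 1% of trials. At 49 per arm, 20% v 40% and mean time to death 3 days, the mean stays are 11.8 v 9.5 days; B is significantly shorter in 31% (Wilcoxon) or 19% (t-test).

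Late deaths, not capped, 49 per arm, 20% v 30% or 40%: with mean time to death 14 days B is shorter in 50–51% of trials, and with 20 days in 35–42%.

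**Step 5: the same scenario with death scored worst.** At 20% v 40% and 3 days, A is significantly better in 41% of trials and B in about 0%. Days alive and out of hospital to day 28 (the window used in this run, death = 0) average 12.3 v 9.2. The direction now agrees with mortality.

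**Step 6: sections 15.3 and 15.4 side by side.** Days on dialysis, on ventilator, in ICU and in hospital are continuous under section 15.3 (t-test or Wilcoxon) and categorical in the quarterly list of section 15.4 (chi-squared). Section 5.1 also keeps them apart from complications (item 4 against item 6), whereas section 15.4 puts them inside the bracket that spells out complications.

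**The case against.** The strongest reply is that the handling of death in a secondary duration is commonly left to the SAP, which section 15 promises and allows to modify the plan. The protocol fixes the test but not the value a death takes; a Wilcoxon test with deaths ranked worst would also fit its wording, and raw counts in the data list do not prevent a derived variable. A SAP could indeed cure the problem. But the endpoint is named as a duration, collected as a duration and tested as a continuous variable, and nothing in the protocol points to any other value. Applied as written, it has this tilt.

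Three stronger readings are tempting, and the document does not support them.

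- A reader might infer that the arm with more deaths must score better on all four measures, and that an early death beats every survivor. It is only a tendency, conditional on early death. A survivor never ventilated or dialysed also scores 0, so the direction is less certain for those two measures, and neither was simulated. The TEG requirement may also remove some of the earliest deaths.
- A reader might infer that quarterly monitoring would hide harm. Section 15.4 names mortality first in the same sentence, section 5.2 lists death among the adverse events compared at the interim analysis, and section 12.5 names increased mortality among its stopping criteria. Deaths are seen beside the durations.
- A reader might infer that section 15.4 leaves the durations without a usable final test. Its opening sentence still sends continuous variables to section 15.3. The conflict is confined to the quarterly list.

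**Conclusion.** The point holds as a tendency. With patients who die included and no rule for them, item 4 favours the arm with more deaths whenever deaths come earlier than survivors' durations would end. The protocol describes death from exsanguination (section 1), which makes early death plausible, but it states no timing and no rate. Under the assumptions shown the false gain is about 2 days of hospital or ICU stay at 20% v 40% mortality and 0.45 ICU days at 25% v 30%. It is zero with equal mortality or with deaths as late as survivors' discharge, and it reverses with later deaths.

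The contradiction between sections 15.3 and 15.4 needs no assumption. Both defects concern secondary or monitoring comparisons; the primary analysis and the sample size are untouched. They should be corrected before the analysis, in the protocol or the SAP.

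**What to change.** - **Item 4:** analyse days alive and free of dialysis, of ventilator, of ICU and of hospital to day 30. Score death by day 30 as 0 (worst rank) and compare arms by the Wilcoxon test.
- **Beside it:** show 30-day mortality and the raw durations in survivors, as descriptive results.
- **After discharge:** state a convention that patients discharged alive count as free of support and out of hospital from discharge, unless a death or readmission is known.
- **Section 15.4:** remove the durations from the chi-squared list, or replace them with yes/no need for dialysis or ventilation, shown next to deaths.

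The cost is small but not nil. Day counts and in-hospital date of death are already collected, and 30-day mortality already needs vital status at day 30. Chart review ends at discharge, however, and most stays are expected to last about 14 days, so the part of the window after discharge rests on the stated convention or on extra follow-up. The other price is that free-days combine mortality and duration, so they cannot be read without their components.

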RATIONALE	Our study will test the feasibility of providing whole blood (WB) for resuscitation of adult male trauma patients in hemorrhagic shock and determine the effects of WB on clinical outcomes as well as the effects on coagulation, fibrinolysis, and inflammation, and hemolytic transfusion reactions compared to standard blood component therapy.
STUDY DESIGN	Prospective cohort study
PRIMARY OBJECTIVE	1. Compare volume of blood transfusion within 24 hours of admission between patients receiving whole blood and standard component therapy.
SECONDARY OBJECTIVES	The study will also compare: 1. Functional coagulopathy as measured by thromboelastography;

	
 2. 30-day mortality; 3. Number of units of blood products transfused by component/product; 4. Complications; 5. Hemolysis; 6. Wastage of blood units.
NUMBER OF PATIENTS	
Whole blood arm - 49 male patients over apparent age 18. Component therapy arm –49 male and female patients over apparent age 18.

PATIENT SELECTION CRITERIA	
Inclusion Criteria:
 
 • Whole blood arm: Male trauma patients over apparent age 18 with massive transfusion activation and presenting systolic blood pressure <100, who are receiving or will receive whole blood for initial resuscitation • Component therapy arm: Male and female trauma patients over apparent age 18 with massive transfusion activation and presenting systolic blood pressure <100, who have received, are receiving or will receive component therapy for initial resuscitation. 
Exclusion Criteria:
 
 • Patients with burns over >20% total body surface area
TEST PRODUCT, DOSE, AND ROUTE OF ADMINISTRATION	
Group O+ whole blood stored at 1-6 °C for up to 10 days. Patients may receive up to 4 units during the initial phase of the proposed study, to be increased to up to 6 units (see 5.2 Safety Evaluations) Product is administered to replace ongoing blood loss and restore/maintain hemodynamic stability and hemostasis. Product will be transfused intravenously as needed during initial traumatic resuscitation only. Following administration of whole blood if further transfusion is needed during initial trauma resuscitation, or after resuscitation is completed, the patient will receive standard

PI: [name]

	component therapy (packed red blood cells, plasma and platelets in a 1:1:1 ratio).

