There have been reports of hemolytic reactions when a patient initially transfused with unmatched group O whole blood later received type-specific transfusion. A similar situation is encountered in current massive transfusion protocols and hemolytic reactions are prevented using the following precautions. Currently when the patient's blood type is unknown during a massive transfusion activation at UCLA, sets of 6 group O PRBC units, 6 pre-thawed group A plasma units and 1 apheresis platelet unit are provided. Once the blood type of the patient is determined, the blood bank switches to providing type-specific products unless the patient's blood type is group B or AB (i.e. incompatible with the group A plasma); under this circumstance, the blood bank provides another set of 6 group O PRBC units and compatible plasma before switching to type specific PRBCs. We have not identified any hemolytic transfusion reactions using this approach. We intend to follow this same practice with the transfusion of low titer group O+ WB. If after receiving low titer group O+ WB the patient's blood type is found to be a type other than group O, the blood bank will provide a set of group O PRBC units and compatible plasma units, before switching to type specific PRBC units.

Providing further evidence of the safety of this approach, our institution participated in a multi-center study evaluating the safety of the use of thawed group A plasma in trauma patients.²⁷ This study evaluated trauma patients that received group A plasma as part of the initial resuscitation (354 B and AB patients and 809 A patients). The two study groups were comparable in terms of age, gender, TRISS probability of survival, and total number of blood products transfused. The study found that the use of group A thawed plasma during the initial resuscitation of injured patients of unknown ABO group was not associated with increased in-hospital mortality, early mortality or hospital length of stay for group B and AB patients compared to group A patients. Additionally, of the 17 participating centers, only 4 (24%) provide low-titer group A plasma; the other 13 centers do not perform titers of the plasma components. This

PI: [name]

experience indicates that transfusion of group A thawed plasma, regardless of anti-B titer, is safe. A manuscript reporting these findings was recently accepted by *Transfusion* (accepted March 15, 2017).

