8.4.1 Dosage/Dosage Regimen

Adult male patients may receive up to 4 units of whole blood if needed during initial traumatic resuscitation in the initial phase of the study, and up to 6 units if deemed to be safe (see section 5.2, Safety Evaluations).

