10 EVALUATIONS BY VISIT

10.1 Visit 1 (Days 1-365)

Hospital Stay visit: typically 1-14 days, but can be as long as one year.

1. Assign the patient a unique study number. This number is planned to be listed on a bracelet in a packet present in the ED. The bracelet will be placed on the patient's wrist during initial admission procedures to identify the patient as a participant in the study.
2. All demographic data, past medical history, and concurrent medications are recorded by hospital staff as part of standard admission procedures. This information will be reviewed by study personnel during analysis.
3. Physical examination, vital signs, and standard clinical labs are performed and recorded by hospital staff.
4. Additional blood samples will be collected for TEG/platelet mapping and CAT (one 4 mL sodium citrate and one 4 mL heparinized tube per draw). This will be performed at the following time points: on admission, after each 6 units of whole blood equivalent (WB or PRBCs) transfused, at 3 and 6 hours of resuscitation, at the time of hemostasis determined by the trauma surgeon, and on ICU days 1,3 and 5.
5. Standard clinical labs including complete blood counts (white blood cell count, hemoglobin, hematocrit, and platelet count), blood chemistries, and standard coagulation labs (prothrombin time, international normalized ratio, partial thromboplastin time) will be performed at least daily as standard of care. This data will also be collected as part of the study. Of note, serial platelet counts obtained

PI: [name]

as standard of care will be monitored no less frequently than daily at noon (see also Schedule of Events).

6. In addition to standard clinical labs, hemolysis labs will be performed as listed above on ICU day 1 which will be billed to the study.
7. Follow up by chart review will continue for the duration of the hospital stay (typically roughly 14 days but can be up to one year).
8. Chart review during the hospital stay will collect the following data:

Data collected on initial 24 hours of hospital stay:

Medical record number

Date of birth /age

Sex

Race

Weight

Height

Injury date/time

Arrival date/time

Emergency Department exit date/time

Operating room arrival time

Tier (defines levels of critical condition for trauma patients)

Injury description

Mechanism of injury

Injury Severity Score

Glasgow Coma Scale and vitals

Intubation status and location of intubation

Whether patient received cardiopulmonary resuscitation

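### Secondary endpoint 5 tests unit counts product by product, so the red cell count is lower in the whole blood arm by substitution even when transfusion need is identical

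*Protocol*

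**What the plan says.** Item 5 of the secondary efficacy endpoints in section 5.1 is "Number of units of blood products transfused by component/product during first 24 hours of admission and total hospitalization". The synopsis lists the matching secondary objective under the words "The study will also compare", so a between-arm comparison is planned and not only a table.

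Section 15.4 refers continuous secondary endpoints back to 15.3, which says: "If the data appears to follow a normal distribution, a t-test will be used, otherwise, a nonparametric Wilcoxon rank sum test will be used".

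On the order of products, section 8.4.1 says "Adult male patients may receive up to 4 units of whole blood if needed during initial traumatic resuscitation" in the initial phase, and "up to 6 units if deemed to be safe". The synopsis adds that standard components follow if more transfusion is needed. Controls receive everything as PRBC, plasma and platelets (section 8.3).

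The protocol does have a red cell equivalence. Section 10.1 schedules thromboelastography (TEG) samples "after each 6 units of whole blood equivalent (WB or PRBCs) transfused", and item 2 of the secondary endpoints does likewise. Item 5 does not use it.

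**The concern.** A whole blood unit carries red cells, plasma and platelets. Counted by product, its natural place is a separate whole blood line, and it adds nothing to the three component lines. Patients in the whole blood arm use up their whole blood allowance before they receive a PRBC unit, while controls receive PRBC from the first unit. The PRBC counts therefore differ by design, and the whole blood count is zero in controls.

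Item 5 sits under efficacy. Section 2.1 says that whole blood may reduce transfusion requirements, and the sample size rests on a reduction in PRBC and plasma transfusions. A significant fall in PRBC units would easily be read as supporting that hypothesis, although substitution alone can produce it.

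**Working it through.** **Inputs from the protocol.** Whole blood cap of 4 units, later up to 6 (8.4.1). Whole blood first, components afterwards (synopsis). Tests as in 15.3. Type I error 0.05, taken as two-sided. 49 enrolled per arm, of whom about 18 have severe TBI: 49 − 18 = 31 in the primary analysis. The protocol states no figure for item 5, so there is none to reproduce.

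**Step 1: arithmetic at equal need.** Let need be the number of red-cell-bearing units a patient requires, the same in either arm.

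- Whole blood units = min(need, cap)
- PRBC, whole blood arm = need − min(need, cap)
- PRBC, control arm = need
- Difference = min(need, cap)
- Whole blood + PRBC = need in both arms

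| Need | PRBC, control | PRBC, whole blood arm, cap 4 | PRBC, whole blood arm, cap 6 |
|---|---|---|---|
| 4 | 4 | 0 | 0 |
| 8 | 8 | 4 | 2 |
| 12 | 12 | 8 | 6 |
| 18 | 18 | 14 | 12 |

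**Step 2: how often this tests significant.** This depends on the distribution of need, which the protocol does not give. Assumption: need = 1 + a Poisson count whose mean is gamma distributed with mean (m − 1) and coefficient of variation (CV) 0.7 or 1.0, for m = 6 to 18. The variance is (m − 1) + [CV × (m − 1)]². The SD then runs from √(5 + 12.25) = 4.2 units (m = 6, CV 0.7) to √(17 + 289) = 17.5 units (m = 18, CV 1.0). Both arms draw from the same distribution, with 31 per arm and 2,000 simulated studies per row (simulation standard error at most about 1 percentage point).

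| Mean need | CV | Cap 4: mean PRBC difference | Wilcoxon | t-test | Cap 6: mean PRBC difference | Wilcoxon | t-test |
|---|---|---|---|---|---|---|---|
| 6 | 0.7 | 3.40 | 98.7% | 92.2% | 4.40 | 100.0% | 99.6% |
| 6 | 1.0 | 3.08 | 95.3% | 65.4% | 4.03 | 99.9% | 88.4% |
| 8 | 0.7 | 3.59 | 88.3% | 72.7% | 4.95 | 99.6% | 95.7% |
| 8 | 1.0 | 3.37 | 82.4% | 46.8% | 4.33 | 97.2% | 70.4% |
| 12 | 0.7 | 3.88 | 59.2% | 46.4% | 5.37 | 88.0% | 73.4% |
| 12 | 1.0 | 3.68 | 53.5% | 25.3% | 4.89 | 80.1% | 43.5% |
| 18 | 0.7 | 3.91 | 29.5% | 22.6% | 5.63 | 58.1% | 44.2% |
| 18 | 1.0 | 3.66 | 28.2% | 14.1% | 5.21 | 51.7% | 23.4% |

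**Step 3: all enrolled patients.** Item 5 is not restricted to patients without severe TBI. The same model with 49 per arm (3,000 studies per setting) gives 40% to 99.9% by Wilcoxon and 18% to 99% by t-test at cap 4, and 70% to 100% and 32% to 100% at cap 6.

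**Step 4: after the change.** Testing whole blood + PRBC in the Step 2 simulations gives Wilcoxon rejection in 3.3% to 5.9% of studies, about the nominal 5%.

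**Step 5: plasma and platelets.** Substitution pushes plasma down in the same way. However, section 2.1 requires 6 further type-specific plasma units before type-specific PRBC in patients given uncrossmatched whole blood, which can offset part or all of a gap of 4 to 6. For platelets the unit is unclear. Section 8.3 describes a 1:1:1 ratio, while section 1.2 says that "sets of 6 group O PRBC units, 6 pre-thawed group A plasma units and 1 apheresis platelet unit are provided". In apheresis units, substitution removes 4/6 = 0.67 of a unit at cap 4 and 6/6 = 1 at cap 6.

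**The case against.** The protocol never says that a whole blood unit counts as no red cells. Counting rules usually belong in the statistical analysis plan, which section 15 promises and which may supply one. Further, fewer component units is a real difference in what item 5 measures. Section 1 names fewer donor exposures as an advantage of whole blood, and total requirement is measured by the primary endpoint and secondary item 1, both of which are volumes. The whole blood count would also stand beside the component counts, so an informed reader could see the substitution.

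Much of this stands. The raw counts are valid description, and they mislead only when read as reduced need. But the protocol already fixes the endpoint, its place under efficacy, the comparison and the test. A plan that followed them faithfully, counting by product, would reproduce the built-in difference.

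Several stronger readings are tempting but unsupported:

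- Every whole blood patient loses exactly 4 or 6 PRBC units. The caps apply only as needed, so patients needing less shift by less. Section 5.2 also has an intermediate step of 5 units.
- Plasma and platelet counts must fall as red cells do. Step 5 of the working shows why this is not established.
- The arms differ only in labelling. The protocol claims fewer donors and less additive volume for whole blood.
- The primary endpoint is distorted too. It is a total volume and does not depend on the split by product.

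**Conclusion.** The point holds for red cells. At equal need, the PRBC count in the whole blood arm is lower by min(need, cap), given the protocol's order of products and provided whole blood is counted as its own product. That needs no outside figure.

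How often the difference tests significant does rest on assumptions. The range in the working is wide because the distribution of need is unknown, and the simulation has every whole blood patient using whole blood up to the smaller of need and cap. Even its lowest value, 14%, is well above 5%. The rates are higher if all 49 per arm are analysed. For plasma and platelets the direction is plausible but the size is not established.

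This affects the interpretation of one secondary efficacy endpoint. It is worth correcting because the result would look like confirmation of the study's hypothesis.

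**What to change.** For item 5, make the tested between-arm comparison the number of red cell units in whole blood equivalents (whole blood + PRBC), at 24 hours and over the hospitalization. Report raw counts of whole blood, PRBC, plasma and platelets by arm descriptively, and state that a lower component count in the whole blood arm is expected from substitution and is not evidence of reduced need. The raw table still shows how many products each arm received, which matters for donor exposure.

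Any plasma or platelet equivalent should be a supportive analysis, labelled approximate, with its conversion and the platelet unit stated. The 6:6:1 issue set in section 1.2 is a dispensing pack and not a measure of platelet content, so a factor taken from it is open to dispute.

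The cost is one accounting rule, with no added data or patients and no change to care. The downside is small: one whole blood unit equals one PRBC unit only approximately, and the text should say so.
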